#### **4.1.5 Follow-up Phase**

All patients are required to complete follow-up assessments, including evaluations of safety, PD, PK, clinical effects, and MRI. Patients will be followed-up for 14 weeks after the last dose (Week 30 for the 2, 4, 8, and 16 mg cohorts and Week 26 for the 32 mg cohort). An early termination (ET) visit will be required in the event of early withdrawal.

## **4.2 SCHEDULE OF ASSESSMENTS**

The schedule of assessments for patients participating in the single and multiple dose portions of the study is presented in [Table 1](#) (2, 4, 8, and 16 mg cohorts) and [Table 2](#) (32 mg cohort). The Schedule of Assessments for patients participating in the multiple-dose portion of the study only is presented in [Table 3](#).

**At each relevant time point, the UHDRS, PBA-s, and Columbia-Suicide Severity Rating Scale (C-SSRS) should be performed prior to other assessments.**

**Table 1 Schedule of Assessments for Patients Participating in Both the Single and Multiple Dose Portions of the Study (2, 4, 8, and 16 mg cohorts)**

Visit	Pre-Screening a	Screening b	Double-Blind Treatment (Single Dose)		Sentinel Patient Follow-up	Follow-up		Double-Blind Treatment (Multiple Dose)			Follow-up		
	1	2	3	4	5	6	7	8 c	9	10	11 or ET	12	13
Week		-4 to 0	0	0	0	2	4	8	12	16	20	28	30
Study Day (Visit Window, if applicable) Event/Assessment		Day -28 to -1	Day -6 to Day 1 (Baseline)	Day 2 (24 ± 4h postdose)	Day 3 (48 ± 4h postdose)	Day 14 (±2)	Day 28 (±3)	Day 56 (±3)	Day 84 (±3)	Day 112 (±3)	Day 140 or ET (±5)	Day 196 (±5)	Day 210 d (EOS) (±5)
Predose/Non-dosing Days													
Patient informed consent form (ICF) Signed	X	X											
Inclusion/exclusion criteria		X	X					X					
Medical history and demographics		X											
Physical examination e		X	X	X	X	X	X	X	X	X	X	X	
C-SSRS f		X	X*			X	X	X*	X*	X	X*		
UHDRS		X	X			X	X	X	X	X	X		
PBA-s		X	X			X	X	X	X	X	X		
Drug screen g		X											
Urine pregnancy test h			X*					X*	X*	X*			
Adverse event monitoring		X	X*	X q	X q	X	X	X*	X*	X*	X	X	X
Prior and concomitant medications		X	X*	X q	X q	X	X	X*	X*	X*	X	X	X
3T MRI of the brain (without contrast)		X					X				X		
Vital signs i		X	X*	X	X	X	X	X*	X*	X*	X	X	
12-lead ECG j		X					X						
Serum pregnancy test h		X											
Clinical laboratory tests k		X	X	X	X	X	X	X	X	X	X	X	
Hepatitis (HBsAg, HCV)		X											
Blood sample for Prescreening assays l	X												
Blood sample for PK m			X	X	X	X	X	X	X	X	X		
Blood sample for immunogenicity n			X				X	X	X	X	X	X	
CSF sample for safety, exposure, and PD o			X*				X	X*	X*	X*	X r	X	
Randomization			X										

Visit	Pre-Screening a	Screening b	Double-Blind Treatment (Single Dose)		Sentinel Patient Follow-up	Follow-up		Double-Blind Treatment (Multiple Dose)			Follow-up		
	1	2	3	4	5	6	7	8 c	9	10	11 or ET	12	13
Week		-4 to 0	0	0	0	2	4	8	12	16	20	28	30
Study Day (Visit Window, if applicable) Event/Assessment		Day -28 to -1	Day -6 to Day 1 (Baseline)	Day 2 (24 ± 4h postdose)	Day 3 (48 ± 4h postdose)	Day 14 (±2)	Day 28 (±3)	Day 56 (±3)	Day 84 (±3)	Day 112 (±3)	Day 140 or ET (±5)	Day 196 (±5)	Day 210 d (EOS) (±5)
Study drug administration via IT injection p			X					X	X	X			
Postdose on Dosing Days	-												
Physical examination e			X					X	X	X			
Adverse event monitoring			X q					X	X	X			
Clinical laboratory tests k			X					X	X	X			
Concomitant medications			X					X	X	X			
Vital signs l			X					X	X	X			
Blood samples for PK m			X							X			
Study completion													X

Abbreviations: AE = adverse event; CAG = cytosine-adenine-guanine; CSF = cerebrospinal fluid; C-SSRS = Columbia-Suicide Severity Rating Scale; ECG = electrocardiogram; EOS = end of study; ET = early termination; h = hour; HBsAg = hepatitis B surface antigen; HCV = hepatitis C virus; ICF = informed consent form; IT = intrathecal; MRI = magnetic resonance imaging; PBA-s = Short Problem Behaviors Assessment; PD = pharmacodynamics; PK = pharmacokinetics; SNP= single nucleotide polymorphism; SNP1 = SNP rs362307 T= thymine; UHDRS = Unified Huntington’s Disease Rating Scale.

Note: The UHDRS, PBA-s, and C-SSRS should be completed prior to any other assessments. Assessments completed predose on Day 1 are considered Baseline.

**\*For each dosing visit (Day 1/Visit 3 [single dose phase]; Day 56/Visit 8; Day 84/Visit 9; and Day 112/Visit 10 [multiple dose phase]), these predose procedures must be performed predose on the day of dosing. All other predose assessments (inclusion/exclusion criteria [Day 1/Visit 3 and Day 56/Visit 8 only], physical examination, UHDRS, PBA-S, clinical laboratory tests [including a blood sample to confirm platelet count and prothrombin clotting time], blood sample for PK, and blood sample for immunogenicity) may be performed up to a week prior to dosing.**

- a Prescreening is only required for patients who do not have documented heterozygosity for SNP rs362307 (SNP1) with the T variant on the same allele as the cytosine-adenine-guanine (CAG) triplet expansion. Prescreening can happen anytime before Screening. It is anticipated that it will take at least 6 weeks to process the results of this testing.
- b Screening assessments can occur on multiple days, provided they are within the 4-week Screening period.
- c There is a minimum washout period of 8 weeks between the first dose and the start of multiple dosing. However, due to the timing of Dose Escalation Committee review to determine if the multiple dose phase can proceed for a dose cohort, the duration between the Week 4 visit and Week 8 visit may be longer than 4 weeks. Investigators will be notified when the Visit 8/Week 8 visit can occur. During this time, a telephone contact for safety follow-up should be performed monthly, at a minimum.
- d Follow-up Day 210 Visit for AE monitoring can be a telephone call.
- e At Screening, physical examination will include (but is not limited to) an examination of skin; head, eyes, ears, nose, throat; respiratory; cardiovascular; gastrointestinal; endocrine, metabolic; blood, lymphatic; musculoskeletal, psychiatric, and neurologic systems. Predose and on Visits 6 (Day 14), 7 (Day 28), 11 (Day 140), and 12 (196) the physical exam must include (at a minimum) head, eyes, ears, nose, throat, respiratory, cardiovascular, gastrointestinal, musculoskeletal, psychiatric, and neurologic systems. Other systems should be evaluated as appropriate. After study drug administration, a targeted physical exam, including the neurologic system (with special attention to the motor system, upper and lower extremity measures of strength, tone, reflexes, and ambulation),

- will be performed 30 minutes ( $\pm 5$  minutes), 1, 2, 3, and 4 hours ( $\pm 15$  minutes) postdose, with an additional exam 24 hours ( $\pm 4$  hours) after the first dose. The sentinel patients in each cohort will also repeat this exam at 8 hours ( $\pm 30$  minutes), 12 hours ( $\pm 2$  hours), 24, and 48 hours ( $\pm 4$  hours).
- f C-SSRS baseline/screening version will be performed at the Screening Visit, and the 'since last visit' version will be performed at all other noted visits.
  - g Urine drug screen for selected drugs of abuse.
  - h For female patients of childbearing potential, a negative serum pregnancy test must be documented at the Screening Visit. On dosing days, a negative urine pregnancy test must be documented predose.
  - i Vital signs include blood pressure, pulse, temperature, weight, and height. On dosing days blood pressure and pulse will be measured at the following time points:  $\leq 30$  minutes predose and 1, 2, and 4 hours ( $\pm 15$  minutes) postdose. Sentinel patients will also have blood pressure and pulse measured 12 hours ( $\pm 2$  hours), 24 and 48 hours ( $\pm 4$  hours) postdose. Weight and temperature will only be measured predose on dosing days. Height will be measured at baseline only. Blood pressure (systolic and diastolic), temperature, and pulse should be measured after patient has been resting quietly for  $\geq 3$  minutes.
  - j Electrocardiogram recordings will be obtained in triplicate in the supine position after the patient has rested comfortably for  $\geq 5$  minutes.
  - k Clinical laboratory safety testing, including clinical chemistry, hematology, and urinalysis. Within 1 week prior to lumbar puncture, a blood sample will be tested to confirm platelet count and prothrombin clotting time. Clinical laboratory safety testing will be performed predose on all dosing days. On Day 1 only, samples for clinical chemistry and hematology measures (CBC, complement, and fibrinogen only) will also be collected at 1 and 4 hours ( $\pm 15$  minutes), and 24 hours ( $\pm 4$  hours) postdose, and for sentinel patients only, 48 hours ( $\pm 4$  hours). On all non-dosing days, clinical laboratory safety testing will be performed just once. On Day 196, only platelet count and prothrombin clotting time need to be assessed (prior to CSF sample). Urinalysis will be performed predose on all dosing days, and once on all other days noted.
  - l Blood samples for the Prescreening assays to determine eligibility.
  - m On Day 1, sentinel patients will have blood samples for PK analysis collected predose, 30 minutes ( $\pm 5$  minutes), 1, 2, 4 hours ( $\pm 15$  minutes), 12 hours ( $\pm 2$  hours), 24 hours and 48 hours ( $\pm 4$  hours) postdose. All other patients will have blood samples for PK analysis collected predose and 30 minutes ( $\pm 5$  minutes), 1, 2, 4 hours ( $\pm 15$  minutes), 12 hours ( $\pm 2$  hours), and 24 hours ( $\pm 4$  hours) postdose on Day 1. On Day 112, all patients will have blood samples collected for PK analysis predose and 1, 2, and 4 hours ( $\pm 15$  minutes) postdose. On all other dosing days, PK samples will be collected predose only. On non-dosing days noted, PK will be collected once.
  - n Blood sample for assessment of antibodies to WVE-120101 will be obtained predose (within 1 week prior to injection) or on non-dosing days, as indicated.
  - o On dosing days, CSF sample will be collected  $\leq 15$  minutes prior to study drug administration. No more than 10 mL of CSF total should be collected. CSF samples must be tested locally for safety for the following parameters: total protein, glucose and cell counts (white blood cell counts with differential) on all noted visits.
  - p Immediately after study drug administration, patients should be active for approximately 30 minutes postdose.
  - q All patients will remain in the clinic and have AEs and concomitant medications recorded through 24 hours postdose. In addition, 2 sentinel patients will remain in the clinic and have AEs and concomitant medications recorded throughout the 48-hour postdose period.
  - r This lumbar puncture is optional for patients who terminate early.

**Table 2 Schedule of Assessments for Patients Participating in Both the single and Multiple Dose Portions of the Study (32 mg Cohort)**

Visit	Pre-Screening a	Screening b	Double-Blind Treatment (Single Dose)		Sentinel Patient Follow-up	Follow-up	Double-Blind Treatment (Multiple Dose)			Follow-up		
	1	2	3	4	5	6	7 c	8	9	10 or ET	11	12
Week		-4 to 0	0	0	0	2	4	8	12	16	24	26
Study Day (Visit Window, if applicable) Event/Assessment		Day -28 to -1	Day -6 to Day 1 (Baseline)	Day 2 (24 ± 4h postdose)	Day 3 (48 ± 4h postdose)	Day 14 (±2)	Day 28 (±3)	Day 56 (±3)	Day 84 (±3)	Day 112 or ET (±5)	Day 168 (±5)	Day 182(EOS) (±5) d
Pre-dose/Non-dosing Days												
Patient informed consent form (ICF) Signed	X	X										
Inclusion/exclusion criteria		X	X				X					
Medical history and demographics		X										
Physical examination e		X	X	X	X	X	X	X	X	X	X	
C-SSRS f		X	X*			X	X*	X*	X*	X		
UHDRS		X	X			X	X	X	X	X		
PBA-s		X	X			X	X	X	X	X		
Drug screen g		X										
Urine pregnancy test h			X*				X*	X*	X*			
Adverse event monitoring		X	X*	X q	X q	X	X*	X*	X*	X	X	X
Prior and concomitant medications		X	X*	X q	X q	X	X*	X*	X*	X	X	X
3T MRI of the brain (without contrast)		X					X			X		
Vital signs i		X	X*	X	X	X	X*	X*	X*	X	X	
12-lead ECG j		X	X	X		X						
Serum pregnancy test h		X										
Clinical laboratory tests k		X	X	X	X	X	X	X	X	X	X	
Hepatitis (HBsAg, HCV)		X										
Blood sample for Prescreening assays l	X											
Blood sample for PK m			X	X	X	X	X	X	X	X		
Blood sample for immunogenicity n			X				X	X	X	X	X	
CSF sample for safety, exposure, and PD o			X*				X*	X*	X*	X*	X	
Randomization			X									
Study drug administration via IT injectionp			X				X	X	X			

Visit	Pre-Screening a	Screening b	Double-Blind Treatment (Single Dose)		Sentinel Patient Follow-up	Follow-up	Double-Blind Treatment (Multiple Dose)			Follow-up		
	1	2	3	4	5	6	7 c	8	9	10 or ET	11	12
Week		-4 to 0	0	0	0	2	4	8	12	16	24	26
Study Day (Visit Window, if applicable) Event/Assessment		Day -28 to -1	Day -6 to Day 1 (Baseline)	Day 2 (24 ± 4h postdose)	Day 3 (48 ± 4h postdose)	Day 14 (±2)	Day 28 (±3)	Day 56 (±3)	Day 84 (±3)	Day 112 or ET (±5)	Day 168 (±5)	Day 182(EOS) (±5) d
Postdose on Dosing Days												
Physical examination e			X				X	X	X			
Adverse event monitoring			X g				X	X	X			
12-lead ECG j			X									
Clinical laboratory tests k			X				X	X	X			
Concomitant medications			X				X	X	X			
Vital signs l			X				X	X	X			
Blood samples for PK m			X						X			
24 hour Urine sample for PK assessments s			X									
Study completion												X

Abbreviations: AE = adverse event; CAG = cytosine-adenine-guanine; CSF = cerebrospinal fluid; C-SSRS = Columbia-Suicide Severity Rating Scale; ECG = electrocardiogram; EOS = end of study; ET = early termination; h = hour; HBsAg = hepatitis B surface antigen; HCV = hepatitis C virus; ICF = informed consent form; IT = intrathecal; MRI = magnetic resonance imaging; PBA-s = Short Problem Behaviors Assessment; PD = pharmacodynamics; PK = pharmacokinetics; SNP= single nucleotide polymorphism; SNP1 = SNP rs362307; T= thymine; UHDRS = Unified Huntington’s Disease Rating Scale.

Note: The UHDRS, PBA-s, and C-SSRS should be completed prior to any other assessments. Assessments completed predose on Day 1 are considered Baseline.

**\*For each dosing visit (Day 1/Visit 3 [single dose phase]; Day 28/Visit 7; Day 56/Visit 8; and Day 84/Visit 9 [multiple dose phase]), these predose procedures must be performed predose on the day of dosing. All other predose assessments (inclusion/exclusion criteria [Day 1/Visit 3 and Day 28/Visit 7 only], physical examination, UHDRS, PBA-S, clinical laboratory tests [including a blood sample to confirm platelet count and prothrombin clotting time], blood sample for PK, and blood sample for immunogenicity) may be performed up to a week prior to dosing.**

- a Prescreening is only required for patients who do not have documented heterozygosity for SNP rs362307 (SNP1) with the T variant on the same allele as the cytosine-adenine-guanine (CAG) triplet expansion. Prescreening can happen anytime before Screening. It is anticipated that it will take at least 6 weeks to process the results of this testing.
- b Screening assessments can occur on multiple days, provided they are within the 4-week Screening period.
- c There is a minimum follow-up period of 4 weeks between the first dose and the start of multiple dosing. However, due to the timing of Dose Escalation Committee review to determine if the multiple dose phase can proceed for a dose cohort, the duration between the Week 4 visit and Week 7 visit may be longer than 4 weeks. Investigators will be notified when the Visit 7/Week 4 visit can occur. During this time, a telephone contact for safety follow-up should be performed monthly, at a minimum.
- d Follow-up Day 182 Visit for AE monitoring can be a telephone call.
- e At Screening, physical examination will include (but is not limited to) an examination of skin; head, eyes, ears, nose, throat; respiratory; cardiovascular; gastrointestinal; endocrine, metabolic; blood, lymphatic; musculoskeletal, psychiatric, and neurologic systems. Predose and on Visits 6 (Day 14), 10 (Day 112), and 11 (168) the physical exam must include (at a minimum) head, eyes, ears, nose, throat, respiratory, cardiovascular, gastrointestinal, musculoskeletal, psychiatric, and neurologic systems. Other systems should be evaluated as appropriate. After study drug administration, a targeted physical exam, including the neurologic system (with special attention to the motor system, upper and lower extremity measures of strength, tone, reflexes, and ambulation), will be performed 30 minutes (±5 minutes), 1, 2, 3, and 4 hours (±15 minutes) postdose, with an additional exam 24 hours (±4 hours) after the first dose. The sentinel patients in each cohort will also repeat this exam at 8 hours (±30 minutes), 12 hours (±2 hours), 24, and 48 hours (±4 hours).
- f C-SSRS baseline/screening version will be performed at the Screening Visit, and the ‘since last visit’ version will be performed at all other noted visits.
- g Urine drug screen for selected drugs of abuse.

- h For female patients of childbearing potential, a negative serum pregnancy test must be documented at the Screening Visit. On dosing days, a negative urine pregnancy test must be documented predose.
- i Vital signs include blood pressure, pulse, temperature, weight, and height. On dosing days blood pressure and pulse will be measured at the following time points:  $\leq 30$  minutes predose and 1, 2, and 4 hours ( $\pm 15$  minutes) postdose. Sentinel patients will also have blood pressure and pulse measured 12 hours ( $\pm 2$  hours), 24 and 48 hours ( $\pm 4$  hours) postdose. Weight and temperature will only be measured predose on dosing days. Height will be measured at baseline only. Blood pressure (systolic and diastolic), temperature, and pulse should be measured after patient has been resting quietly for  $\geq 3$  minutes.
- j Electrocardiogram recordings will be obtained in triplicate in the supine position after the patient has rested comfortably for  $\geq 5$  minutes. Within 24 hours predose on Day 1, 12-lead ECGs will be performed (3 measurements within 1 hour). Postdose, 12-lead ECGs (triplicate) will be performed 1, 2, 4, and 24 hours ( $\pm 15$  mins) after dose administration. ECGs should be performed prior to blood draws, vital signs, or functional assessments.
- k Clinical laboratory safety testing, including clinical chemistry, hematology, and urinalysis. Within 1 week prior to lumbar puncture, a blood sample will be tested to confirm platelet count and prothrombin clotting time. Clinical laboratory safety testing will be performed predose on all dosing days. On Day 1 only, samples for clinical chemistry and hematology measures (CBC, complement, and fibrinogen only) will also be collected at 1 and 4 hours ( $\pm 15$  minutes), and 24 hours ( $\pm 4$  hours) postdose, and for sentinel patients only, 48 hours ( $\pm 4$  hours). On all non-dosing days, clinical laboratory safety testing will be performed just once. On Day 168, only platelet count and prothrombin clotting time need to be assessed (prior to CSF sample). Urinalysis will be performed predose on all dosing days, and once on all other days noted
- l Blood samples for the Prescreening assays to determine eligibility.
- m On Day 1, sentinel patients will have blood samples for PK analysis collected predose, 30 minutes ( $\pm 5$  minutes), 1, 2, 4 hours ( $\pm 15$  minutes), 12 hours ( $\pm 2$  hours), 24 hours and 48 hours ( $\pm 4$  hours) postdose. All other patients will have blood samples for PK analysis collected predose, and 30 minutes ( $\pm 5$  minutes), 1, 2, 4 hours ( $\pm 15$  minutes), 12 hours ( $\pm 2$  hours) and 24 hours ( $\pm 4$  hours) postdose on Day 1. On Day 84, all patients will have blood samples collected for PK analysis predose and 1, 2, and 4 hours ( $\pm 15$  minutes) postdose. On all other dosing days, PK samples will be collected predose only. On non-dosing days noted, PK will be collected once.
- n Blood sample for assessment of antibodies to WVE-120101 will be obtained predose (within 1 week prior to injection) or on non-dosing days, as indicated.
- o On dosing days, CSF sample will be collected  $\leq 15$  minutes prior to study drug administration. No more than 10 mL of CSF total should be collected. CSF samples must be tested locally for safety for the following parameters: total protein, glucose and cell counts (white blood cell counts with differential) on all noted visits.
- p Immediately after study drug administration, patients should be active for approximately 30 minutes postdose.
- q All patients will remain in the clinic and have AEs and concomitant medications recorded through 24 hours postdose. In addition, 2 sentinel patients will remain in the clinic and have AEs and concomitant medications recorded throughout the 48-hour postdose period.
- r This lumbar puncture is optional for patients who terminate early.
- s On Day 1, all patients will have urine samples for PK analysis collected at 0 to 4 hours, 4 to 8 hours, and 8 to 24 hours postdose.

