### **6.2.2 Administration of Study Drug and Collection of CSF**

Study drug (WVE-120101 or placebo) will be administered as a single dose followed by multiple doses (3 doses at 4-week intervals). The route of administration will be IT by direct lumbar injection, and the total volume of the injection will be 10 mL. The lumbar puncture will be performed by an appropriately trained individual. Within 1 week prior to the lumbar puncture, a blood sample will be tested locally for platelet count and prothrombin time to confirm that it is safe to proceed with the lumbar puncture ([Section 8.2.6](#)). Patients should not be sedated during administration of study drug. Detailed instructions on the procedure to be used for lumbar puncture are provided in the Study Operations Manual.

Within  $\leq 15$  minutes prior to administration of study drug, CSF samples will be collected for safety assessments ([Section 8.2.7](#)), exposure ([Section 8.3](#)), and PD ([Section 8.4](#)), per the Schedule of Assessments ([Table 1](#), [Table 2](#), and [Table 3](#)). Additional CSF collected will be stored and used for research purposes. No more than 10 mL of CSF total should be collected.

Immediately after each administration of study drug, all patients should be ambulatory and active for approximately 30 minutes postdose. The Investigator should note any subtle weakness or fatigue during this period. In addition, formal physical examinations targeting the neurological system, will be performed at the time points noted in the Schedule of Assessments ([Table 1](#), [Table 2](#), and [Table 3](#)). Any postdose SAEs will be monitored until resolution.

Cerebrospinal fluid samples will only be used by the Sponsor and/or a contracted vendor for research related to the development of treatments for HD and will be stored for a maximum of 10 years. All biological material will be stored and secured in a way that ensures that unauthorized access is prohibited and the samples are not lost, deteriorated, or destroyed accidentally or illegally. Detailed instructions for sample collection, storage, processing, and shipping will be provided in the Laboratory Manual.

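### The schedules let the predose plasma PK sample be drawn up to a week before dosing, so after the first dose it may miss the end of the dosing interval and the same-day CSF sample

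*Combined protocol and SAP*

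**What the plan says.** The notes under Tables 1, 2 and 3 in protocol Section 4.2 split predose procedures into two groups.

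- For starred items, "these predose procedures must be performed predose on the day of dosing". CSF is starred at every dosing visit. Section 6.2.2 fixes its timing in minutes: "minutes prior to administration of study drug, CSF samples will be collected for safety assessments", with a limit of 15 minutes.
- Unstarred items may be done earlier. The plasma PK sample is unstarred and is named in that list: "blood sample for PK, and blood sample for immunogenicity) may be performed up to a week prior to dosing". The sentence is the same in all three tables and is not limited to the first dose.

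The PK footnotes (m in Tables 1 and 2, l in Table 3) read differently. Table 1 footnote m says "On Day 112, all patients will have blood samples collected for PK analysis predose and 1, 2, and 4 hours" and, for dosing days other than the first and last, "On all other dosing days, PK samples will be collected predose only". The immunogenicity footnotes repeat the one-week window; the PK footnotes do not.

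For other visits the rule is "On non-dosing days noted, PK will be collected once". Day 28 is such a visit at 2 to 16 mg (Table 1) but a dosing visit at 32 mg (Table 2). Section 8.3 records the date and time of each sample.

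**The concern.** Before the first dose there is no drug to measure, so the allowance does no harm there, or at the first dose of treatment-naive patients. From the second dose on, the predose sample is the plasma value nearest the end of the preceding interval. On Days 56 and 84 at 2 to 16 mg, and Days 28 and 56 at 32 mg, it is the only plasma sample for patients who took part in both portions.

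Plasma PK and CSF exposure are both secondary objectives (Section 3.1), and Section 10.4 summarises concentrations in both fluids. If sites may choose any day in a week, part of the spread in predose plasma values reflects scheduling, and a plasma value reported beside a CSF value may come from a different day.

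The allowance also falls unevenly across doses. At Day 28 it can move the plasma sample only in the 32 mg cohort. While plasma is declining, an early draw there would raise the value after the first dose. The matching value after the last dose comes from Day 112, a non-dosing visit that the allowance does not cover.

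**Working it through.** The plan gives no figure of its own to reproduce. The check is day arithmetic on the schedules, then an illustration of size.

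**Inputs.** Nominal interval in the multiple-dose portion: 28 days (Section 4.1). Visit window at dosing visits after the first: ±3 days (Tables 1 to 3). Allowance: 7 days (table notes). Minimum gap before the second dose: 8 weeks at 2 to 16 mg (Table 1, footnote c) and 4 weeks at 32 mg (Table 2, footnote c).

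**Time from previous dose to predose plasma sample**

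| Case | As written | Same-day plasma |
|---|---|---|
| Monthly doses, nominal | as early as 28 − 7 = 21 days | 28 days |
| Monthly doses, both visit windows used | 28 − 3 − 3 − 7 = 15 to 28 + 3 + 3 = 34 days | 28 − 3 − 3 = 22 to 34 days |
| Visit 8 at 2 to 16 mg | as early as 56 − 7 = 49 days | 56 days nominal |

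Seven days is 7/28 = 25% of the monthly interval.

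**Plasma-CSF gap at a dosing visit.** CSF is drawn within 15 minutes before dosing and plasma from 0 to 7 days before, so the two can be up to 7 days apart.

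**Day 28 across cohorts**

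- 2 to 16 mg: non-dosing visit, so 28 ± 3 gives Day 25 to 31.
- 32 mg: dosing visit. With the 4-week minimum, the earliest plasma is about 28 − 7 = Day 21, which is 25 − 21 = 4 days before the earliest permitted elsewhere. The latest is Day 31, or later if the visit is delayed as footnote c allows.

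**Size of the effect.** With first-order decline, the value drawn 7 days early divided by the value on the day is 2^(7/half-life). The half-lives are assumptions.

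| Assumed half-life (days) | Ratio |
|---|---|
| 7 | 2^1 = 2.00 |
| 14 | 2^0.5 = 1.41 |
| 28 | 2^0.25 = 1.19 |
| 56 | 2^0.125 = 1.09 |

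**Effect on the planned multiple-dose parameters (Table 9).** After the last dose, samples are predose, 1, 2 and 4 hours, then the non-dosing visit 28 days later. By the trapezoidal rule the predose value enters AUC over the interval only through the 0 to 1 hour piece, with weight 0.5 h out of 28 × 24 = 672 h: 0.5/672 = 0.07%. Cmax and tmax should rest on the postdose samples.

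**The case against.** The strongest reply is that little of the planned analysis depends on these samples. Table 9 lists no trough parameter, Section 10.4 compares PK parameters across doses, and those parameters barely move. That stands, and it limits the point to by-visit concentrations, pairing at dosing visits and the Day 28 comparison.

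A second reply is that the note permits early sampling without requiring it, and the PK footnotes suggest same-day draws. Also true. But a site following the note complies with the protocol, and nothing says which text governs.

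A third is that sample times are recorded. They support an analysis by actual time, but cannot supply a same-day pair or an end-of-interval value that was never drawn.

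A fourth concerns the illustration: its largest ratio matters least in absolute terms. At a 7-day half-life only 2^(−28/7) = 1/16 of a declining concentration is left at 28 days. This is fair, and with no half-life in the documents the range cannot be narrowed.

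Three stronger readings are tempting and are not supported:

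- A reader might infer that these predose samples are the only evidence on accumulation or on the plasma-CSF relation. They are not. Postdose samples follow the first and last doses, and plasma and CSF are both scheduled at non-dosing visits (Day 28 and Day 140 at 2 to 16 mg, Day 112 at 32 mg).
- A reader might subtract the −3-day window as well and put the earliest 32 mg sample at Day 18. Footnote c of Table 2 stands against that: "There is a minimum follow-up period of 4 weeks between the first dose and the start of multiple dosing". The window and the minimum do not agree and must be reconciled; Day 21 is the safer figure.
- A reader might conclude that the Day 28 comparison is biased upward at 32 mg. Visit 7 can also be delayed, so that sample may be late as well as early, and the direction is not established.

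**Conclusion.** The point holds as a gap in what the schedules guarantee, together with an inconsistency between the table notes and the PK footnotes. After the first dose the plan secures neither an end-of-interval plasma value nor a plasma sample on the same day as the CSF at dosing visits, and at Day 28 it does not secure a common plasma sampling window across cohorts.

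The day counts follow from the schedules alone. The 1.09- to 2.0-fold range rests on assumed half-lives of 56 to 7 days, first-order decline and a draw a full 7 days early; smaller departures give smaller ratios. The primary safety endpoint and the CSF measurements are untouched. This is a modest flaw in a secondary objective, worth correcting because the correction is cheap.

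**What to change.** In Tables 1, 2 and 3, star the PK blood sample at every dosing visit after the patient's first dose, and remove it from the up-to-a-week-early list for those visits. The note then agrees with the PK footnotes, and plasma is drawn before drug on the same day as CSF. The one-week allowance can stay for the other unstarred procedures. In the analysis, summarise predose concentrations by actual time since the last dose, because the ±3-day windows still leave a span of 22 to 34 days.

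The cost is a change to the schedule notes and at most one extra venepuncture, where a site would otherwise have combined the PK draw with the early platelet and prothrombin sample. The patient is already in the clinic that day for predose vital signs and the lumbar puncture.
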